9.2.2.2 Per Protocol (PP) Population

The PP population will comprise all patients in the ITT population (or mITT for imaging-based endpoints) who also have no major protocol violations during the study. This population will be finalized prior to the final lock and primary analysis of the study data. Efficacy analyses will be conducted on this population in support of the primary efficacy results.

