4.3 Study Duration

Study duration is 12 months for each subject with the day of catheter placement/ start of infusion

being designated as Day 0.

Post-treatment follow-up assessment of safety will be performed 14 days after CED infusion.

Thereafter, efficacy and safety assessments will be performed at 30, 60, 90 and 120 days after

CED infusion and every 8 weeks thereafter until 360 days of active follow up have been

completed. Subjects who discontinue before the Day 360 visit will undergo all the procedures

scheduled for the Day 360 visit at the time of discontinuation.

Subjects who complete the Day 360 assessment without confirmed disease progression or

discontinue early without confirmed disease progression will continue to be followed for disease

status until progression where possible. After confirmed progression (on study or during post-

study follow-up), subjects will continue to be followed, where possible, for survival, post-study

treatment(s) for GB and imaging for GB until death (or termination of data collection by the

Sponsor or withdrawal of consent by the subject).

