9.2.2.1 Intent to Treat (ITT)

An ITT population will comprise all subjects who receive any amount of study drug will be used for the primary efficacy analyses, other purely survival-based endpoints and all safety analyses.

A modified ITT population for secondary imaging-based analyses, including PFS, (mITT, see below) will comprise all subjects who receive any amount of study drug and have adequate imaging or clinical data for the ORR analysis. NOTE: Patients who expire or progress clinically prior to the first MRI examination will not be evaluable for any of the response assessments.

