5.2 Modified Intent to Treat Population (mITT)

A modified ITT population for secondary response analyses (mITT) will comprise all subjects who receive any amount of study drug and have adequate imaging (at least 1 post-treatment scan) and clinical data for the ORR analysis.

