5.3 Per Protocol Population (PP)

The PP population will comprise all subjects in the mITT population who also have no major protocol violations during the study. Efficacy analyses will be conducted on this population in support of the primary efficacy results.

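### The per-protocol set excludes on major violations at any time in the 12-month study; if post-infusion events count as major, per-protocol OS can be biased in a direction that is not fixed

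*Protocol*

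**What the plan says.** The primary OS analysis is on ITT. Protocol 9.2.2.1 reads: "An ITT population will comprise all subjects who receive any amount of study drug will be used for the primary efficacy analyses".

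The PP set is supportive. Protocol 9.2.2.2 takes ITT subjects (mITT subjects for imaging-based endpoints) "who also have no major protocol violations during the study" and gives the set this role: "Efficacy analyses will be conducted on this population in support of the primary efficacy results". On timing it says: "This population will be finalized prior to the final lock and primary analysis of the study data".

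The protocol synopsis and SAP 5.3 apply the same violation rule to a different base. The SAP wording is: "The PP population will comprise all subjects in the mITT population who also have no major protocol violations during the study". Under SAP 5.2 a subject in mITT must "have adequate imaging (at least 1 post-treatment scan) and clinical data for the ORR analysis".

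On the time scale, Protocol 4.3 states: "Study duration is 12 months for each subject with the day of catheter placement/ start of infusion", which is Day 0. OS is counted from the start of infusion (Protocol 9.2.5.1) or from catheter placement (SAP 7.7.1). The infusion is planned to last 24 to about 48 hours.

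Neither document lists which violations are major, gives an expected rate, or limits the exclusion to violations known by the end of infusion. Protocol 7.5 says only that delays for weekends, public holidays or weather are not violations. SAP 7.3 says only that major deviations will be summarised by category.

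**The concern.** An analysis of OS from Day 0 should select subjects on facts known at or near Day 0. This rule can select on facts arising up to a year later. Protocol 7.8 prohibits other anti-neoplastic therapy, radiotherapy and investigational therapy during participation, and Table 7 requires visits and MRIs to Day 360. A breach of either can occur only while the subject is alive and on study. If such breaches count as major, longer time on study means more opportunity to be removed.

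PP is the only set named as supporting the primary OS result. There is also no control arm in which the same exclusion could offset itself: PP OS would be read against a fixed 8-month reference, so a shift caused by selection falls entirely on that comparison. Agreement or disagreement between PP and ITT could then reflect the exclusion rule and not the drug.

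**Working it through.** **The plan's own figure.** Protocol 9.1 claims over 80% power with 46 evaluable subjects (exponential OS, medians 8 and 11.5 months, one-sided 10%, 12 months of follow-up). Accrual length is not given. Normal-approximation versions of the exponential test give 0.76–0.79 with 12 months of uniform accrual, 0.78–0.81 with 18 and 0.80–0.82 with 24. A simulated one-sample log-rank test gives 0.77 at 12 months and 0.80 at 24. The claim is reproduced if accrual took about 18 months or more.

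**Assumptions not in the documents.** Major violations arise at ν = 0.02 per month, unrelated to prognosis. PP is drawn from ITT, as in Protocol 9.2.2.2.

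**Case A: violations possible until death or month 12.** With λ = ln 2 / median, the fraction kept in PP is

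K = λ/(λ+ν) × (1 − e^(−12(λ+ν))) + e^(−12(λ+ν)),

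and the PP median (if below 12) is

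M = −ln(1 − K(λ+ν)/(2λ)) / (λ+ν).

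- Median 8: λ = 0.08664 and λ+ν = 0.10664. K = 0.8125 × 0.7219 + 0.2781 = 0.865, so about 14% are removed. M = −ln(0.4679)/0.10664 = **7.1 months**.
- Median 11.5: λ = 0.06027 and λ+ν = 0.08027. K = 0.7509 × 0.6184 + 0.3816 = 0.846, so about 15% are removed. M = −ln(0.4367)/0.08027 = **10.3 months**.

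**Case B: violations possible only until progression.** Protocol 4.4 lists confirmed progression and the start of recurrent-GB treatment as reasons for withdrawal. After that, follow-up is by records or telephone (7.5.5). Take PFS as exponential with the 4-month null median of Protocol 9.2.5.2, and add exponential post-progression survival set so that median OS is 8.0 or 11.5. At the same ν, simulation gives about 9% removed and PP medians of **7.6 and 11.1 months**. Withdrawal independent of death, also at a median of 4 months, gives 7.7 and 11.2.

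**The gradient.** With a true median of 8 months and a 20% chance of violation over 12 months (ν = −ln(0.8)/12 = 0.0186):

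| | Removed, died before month 6 | Removed, alive at month 12 | PP median |
|---|---|---|---|
| No withdrawal | 4.9% | 20.0% | 7.2 |
| Withdrawal, median 4 months | 3.7% | 8.8% | 7.7 |

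Over a 10–30% chance of violation, the PP median is 7.6–6.7 without withdrawal and 7.9–7.6 with it.

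**Base population.** Now nest PP in mITT. With no violations, losing every death before w months moves an exponential median from 8 to 8 + w. Combined with the 20% violation chance:

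| Deaths lost before | Share lost, 1 − e^(−0.08664w) | PP median, no withdrawal | PP median, withdrawal |
|---|---|---|---|
| 0.25 month | 2.1% | 7.5 | 8.0 |
| 0.5 month | 4.2% | 7.7 | 8.3 |
| 1 month | 8.3% | 8.3 | 8.8 |

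The net shift can fall on either side of 8.0.

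**If a test were run on PP.** The plan specifies none, so this only scales the effect. At 46 treated, 20 months of accrual, ν = 0.02 and PP from ITT, power at 11.5 months falls from about 0.80 to about 0.59 (Case A), or to about 0.73 with withdrawal at a median of 4 months. Under the null, with 12 months of accrual and the 20% violation chance, rejection falls from 0.09 to 0.04–0.07. If PP is nested in mITT and all deaths before one month are lost, it rises to 0.12–0.19.

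**With the rule limited to the end of infusion.** Removing 20% of subjects independently of later survival leaves the median at 8.0.

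**The case against.** The strongest reply is that nothing shows the problem will arise. With one short infusion, the violations a sponsor would call major may well be eligibility or administration failures, fixed by about Day 2 and not dependent on later survival time. The set is to be finalised before lock, so the list can be settled then. The primary analysis is on ITT, and the hierarchy in Protocol 9.4 contains no PP test, so no decision rests on this set. Withdrawal at progression also shortens the time at risk.

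Most of this stands. It makes the bias conditional, roughly halves the shift in the null median at the rate used (0.4 months instead of 0.9), and leaves the primary test untouched. It does not remove the mechanism: the exclusion has no time limit in any of the three places it appears. Finalising the set before lock in an open-label study also does not ensure that exclusions are judged without sight of survival.

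A reader might infer more: that long survivors are preferentially removed and PP OS is therefore biased downward. The documents do not support that. They neither define major nor give a rate. Violations driven by clinical decline, such as missed scans in failing subjects, would remove short survivors instead, and nesting in mITT can lose early deaths. Both push PP OS upward.

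**Conclusion.** The point holds as a conditional weakness in a supportive analysis. As written, PP membership may depend on events up to Day 360. If any post-infusion events are classed as major, PP OS can differ from ITT OS for reasons unrelated to the drug.

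At 0.02 violations per month, unrelated to prognosis and with PP drawn from ITT, the shift is about 0.4 months when risk stops at progression (8.0 to 7.6, 11.5 to 11.1). It is 0.9 to 1.2 months when risk runs to death or month 12 (8.0 to 7.1, 11.5 to 10.3). The violation rate, time to withdrawal, accrual length and share of early deaths lost from mITT are all assumptions. Under the synopsis and SAP definition, even the sign is open.

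It would be wrong to infer that the primary conclusion is compromised, since ITT carries it. What is lost is the ability to read PP agreement or disagreement as evidence about that conclusion. It is worth correcting before lock.

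**What to change.** In Protocol 9.2.2.2, the synopsis and SAP 5.3, define PP for OS as ITT subjects with no major protocol violation at or before the end of the first CED infusion, meaning eligibility or study-drug administration violations. The word first is needed because the synopsis and SAP 3.3 allow a second administration. List the qualifying violations before lock. Report later violations by category without using them to exclude anyone from Day 0. Using ITT as the base in all three places also removes the conflict between Protocol 9.2.2.2 and the other two definitions.

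A sensitivity analysis that censors OS at the first later violation is best left out. If kept, label it exploratory, because that censoring is informative when violations follow clinical decline.

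The cost is a sentence or two in each place and no new data. The downside is that subjects with late violations stay in PP, so it differs less from ITT.

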9.2.2.3 IL4R Analysis Population

The IL4R Analysis Population will be the same as the ITT Population, excluding patients who do not have archived tissue or adequate tissue available for analysis, and will be used for efficacy analyses in subgroups according to IL4R expression status (Section 9.2.9).

9.2.2.4 Safety Population

The Safety population will comprise all patients treated on study. Safety analyses will be presented on this population.

9.2.3 Missing Data

All available data will be used, and no efficacy data will be imputed. Procedures for handling missing dates will be described in the statistical analysis plan. For the analyses of response, subjects with baseline assessments but no post-treatment assessments will be counted as non-responders. For time to event variables, patients not known to have experienced an event at the time of analysis will be censored as specified in Section 9.2.5.2.

9.2.4 Baseline and Demographic Characteristics

Baseline and demographic characteristics will be summarized and presented descriptively.

9.2.5 Analysis of Efficacy

Details of all planned efficacy analyses and methods will be published in the SAP (statistical analysis plan) prior to database lock.

9.2.5.1 Primary Efficacy Variable

OS will be defined as the time (in weeks) from start of the CED infusion until death from any cause. Subjects not know to have died at the time of the analysis will be censored at the time of last contact.

OS and will be summarized using the Kaplan-Meier method and tested using a single sample one sided log-rank test on a 10% significance level with null hypothesis of OS 8 months and alternative hypothesis of OS > 8 months.

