4.1 Number of Subjects

Approximately 52 subjects with recurrent or progressive GB will be enrolled in order to achieve 46 evaluable subjects for the primary survival analyses.

Version: v.6.1

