9.1 Determination of Sample Size

The sample size is calculated for the primary analysis and based on the following assumptions: uniform accrual over time, no loss to follow-up, exponentially distributed death times, use of the exponential MLE test, follow-up time 12 months and a one-sided test on a 10% significance level. With a null hypothesis of a median OS of 8 months and an alternative hypothesis of 11.5 months the power for the primary test will be over 80% with 46 evaluable subjects.

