9.2.5.2 Secondary Efficacy Variables

Secondary efficacy variables will include OS variants, ORR and PFS.

ORR will be presented as the percentage of subjects with CRs or PRs by the RANO-based criteria, including those incorporating advanced imaging modalities; only confirmed responses will be presented (i.e., those observed on 2 consecutive MRI scans not less than 4 weeks apart and at appropriate interval following discontinuation of bevacizumab if response was not observed prior to use of bevacizumab).

PFS will be summarized using the Kaplan-Meier method. PFS will be assessed using a single sample log-rank test (against historical control) at 10% significance level with null hypothesis of mPFS 4 months and alternative hypothesis of mPFS > 4 months. PFS will be defined as the time

(in weeks) from start of the CED infusion until radiologic or neurologic disease progression or death from any cause. Subjects not know to have died or experienced disease progression at the time of the analysis will be censored at the time of the last radiologic assessment demonstrating lack of progression or, if during the follow-up period, the time of last contact indicating lack of progression.

Graphical displays and incidence estimates will show PFS and OS at 6, 9, and 12 months.

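### The one-sample log-rank test is planned without a named variance; in its usual form it would run at about 9%, not 10%, and give up 1.5 to 1.9 points of power at 46 subjects

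*Protocol*

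**What the plan says.** - **Primary test.** Protocol 9.2.5.1 has OS "tested using a single sample one sided log-rank test on a 10% significance level", with a null of 8 months. The synopsis and the opening of section 9 describe the same test. None of them gives the variance, the critical value, or an exact or small-sample method.
- **PFS.** Protocol 9.2.5.2: "PFS will be assessed using a single sample log-rank test (against historical control) at 10% significance level", with a null median of 4 months. The synopsis and section 9.4 make this test one-sided. Under 9.4, PFS and the secondary endpoints are tested only if OS succeeds.
- **Sample size.** Protocol 9.1 assumes "uniform accrual over time, no loss to follow-up, exponentially distributed death times, use of the exponential MLE test". The level is one-sided 10% and subjects are followed for 12 months. The section concludes that "the power for the primary test will be over 80% with 46 evaluable subjects". The accrual period is not given.
- **Numbers.** Protocol 4.1: "Approximately 52 subjects with recurrent or progressive GB will be enrolled in order to achieve 46 evaluable subjects". The ITT set is everyone who receives any study drug (Protocol 9.2.2.1, SAP 5.1).
- **SAP.** Protocol 9.2.5 defers details to the SAP. SAP 7.7.1 and 7.7.2 give Kaplan-Meier estimates and confidence intervals for OS and PFS, but no log-rank test, null value, significance level or variance.

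**The concern.** The usual one-sample log-rank statistic compares observed deaths O with the number E expected under the null and divides by √E. When survival is better than the null, subjects accumulate more follow-up, so E grows along with the difference E−O and the divisor shrinks the statistic. With some 30 to 40 deaths this makes the test conservative in the direction the trial cares about, and part of the allowed 10% goes unused.

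Unused error rate is lost power. The design claims only just over 80%, and OS is the gate for every later test. Because the variance is left open, it is also an analyst's choice that could decide a borderline result.

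**Working it through.** **Inputs from Protocol 9.1.** N = 46; one-sided 10%, z = 1.2816; medians 8 and 11.5 months, exponential, so λ0 = ln2/8 = 0.0866, λ1 = ln2/11.5 = 0.0603 and hazard ratio 8/11.5 = 0.696; no loss to follow-up; 12 months' follow-up. The primary analysis waits at least until all subjects have completed or discontinued before Day 360, and censoring is at last contact. I therefore read 12 months as the minimum follow-up after the last entry.

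**Assumed.** Uniform accrual over A = 0 to 30 months.

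**Step 1: the plan's own figure.** Expected deaths are d = N × [1 − (e^(−12λ) − e^(−(12+A)λ))/(Aλ)]. Power of the exponential MLE test on the log-hazard scale is Φ((ln(λ0/λ1) − z/√d0) × √d1).

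At A = 18: d0 = 46 × (1 − 0.179) = 37.8 and d1 = 46 × (1 − 0.296) = 32.4. Power = Φ((0.363 − 1.2816/√37.8) × √32.4) = Φ(0.88) = 81.0%.

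Other accruals give 73.3% (A = 0), 76.9% (6), 79.3% (12), 82.2% (24) and 83.2% (30). The stated figure therefore reproduces once accrual is somewhere between 12 and 18 months or longer.

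**Step 2: size and power of the log-rank test.** For each simulated trial, E = λ0 × total follow-up time. Reject if (E−O)/√V > 1.2816, with V = E (usual) or V = (O+E)/2. There were 1,000,000 trials per cell (Monte Carlo standard error about 0.03 points for size, 0.04 for power). N = 46:

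| Accrual (months) | Deaths, null / alternative | Size, V=E | Size, V=(O+E)/2 | Power, V=E | Power, V=(O+E)/2 | Gain (points) |
|---|---|---|---|---|---|---|
| 0 | 29.7 / 23.7 | 9.06% | 10.35% | 70.6% | 73.2% | 2.5 |
| 6 | 33.3 / 27.3 | 9.0% | 10.2% | 74.8% | 76.9% | 2.1 |
| 12 | 35.9 / 30.1 | 9.0% | 10.1% | 77.5% | 79.4% | 1.9 |
| 18 | 37.8 / 32.4 | 8.9% | 10.0% | 79.4% | 81.1% | 1.7 |
| 24 | 39.2 / 34.2 | 8.8% | 9.9% | 80.6% | 82.3% | 1.6 |
| 30 | 40.2 / 35.7 | 8.8% | 9.9% | 81.5% | 83.1% | 1.5 |

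Repeat runs with fewer trials agree to about 0.1 to 0.2 points. At 18 months the usual test needs 48 to 49 subjects (80.6%, 81.4%) to match the averaged variance at 46, so the gain is worth about 3 subjects.

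**Step 3: why the formula and the simulation differ.** When simulated at A = 18, the exponential MLE test itself has size 8.8% and power 79.3%, almost the same as the usual log-rank test. The 81.0% from the formula is a normal approximation that overstates power at this number of deaths.

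**Step 4: 52 treated.** With V = E, power is 81.3, 83.1, 84.2 and 85.1% at 12, 18, 24 and 30 months' accrual. With (O+E)/2 it is 82.9, 84.5, 85.6 and 86.3%. The gain is 1.2 to 1.6 points and all eight figures exceed 80%.

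**Step 5: PFS.** With a null median of 4 months, N = 46 and continuously observed exponential times, the size is about 8.7% with V = E and 9.6 to 9.9% with (O+E)/2 for accrual of 12 to 24 months.

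**Step 6: alternatives.** Keeping V = E with a critical value of 1.22 gives size 9.9 to 10.1% for OS at 12 to 30 months' accrual and 10.1 to 10.2% below that. V = O is unsuitable: its size is 10.9 to 11.8%.

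**The case against.** **The plan names no variance, so 8.9% is not a property of the plan.** This stands. A reader might infer that the trial's test runs at 8.9%, but the documents do not support that. The figure describes the usual statistic, if that is what gets programmed. What can be shown from the documents is that the choice is open.

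**The error is on the safe side.** This also stands. A size of about 9% against an allowed 10% cannot inflate false claims, and some statisticians would accept the margin in a single-arm comparison with a fixed historical median.

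**It does not in general decide whether power exceeds 80%.** A reader might infer that it does. At N = 46 it does so in one of the four assumed accruals from 12 to 30 months. One more subject (N = 47, 18 months) brings the usual test to about 80.0 to 80.1%. If all of the approximately 52 are treated, both versions exceed 80% at 12 months' accrual or more. The documents give neither the accrual period nor the number who will be treated.

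**The change is not free.** With short accrual the averaged variance exceeds the nominal level: 10.2% at 6 months and about 10.4% with no accrual spread. Calibration to the actual accrual removes this.

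**The PFS figure is rough.** Progression is seen at scheduled scans, and Protocol 9.2.2.1 puts PFS on the mITT set, whose size is not stated. The model ignores both.

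**The missing test in the SAP matters more.** Agreed. Naming the variance is one line within that repair.

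**Conclusion.** The point holds as a minor improvement. The one-sample log-rank test is specified without a variance, is absent from the SAP, and is not the test behind the section 9.1 power. If (O−E)/√E is used with 46 subjects, the actual one-sided size for OS is about 8.8 to 9.1% across all accrual patterns tried. For PFS it is about 8.7% under a simplified model. The cost is 1.5 to 1.9 points of OS power for accrual of 12 to 30 months, or 1.2 to 1.6 points with 52 treated.

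The size shortfall does not depend much on accrual. Crossing 80% does: it happens at 18 months with 46 subjects, but not at 12, 24 or 30 months, nor with 52 subjects at 12 months or more. It would be wrong to conclude that the stated power is unattainable or that a positive OS result would be in doubt.

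These results assume exponential survival, uniform accrual and no loss to follow-up (all from section 9.1), together with the assumed accrual range.

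**What to change.** 1. State the one-sample log-rank test for OS and PFS in Protocol 9.2.5.1 and 9.2.5.2 and in SAP 7.7.1 and 7.7.2, with its null median, one-sided 10% level and statistic.
2. Use variance (O+E)/2, or keep variance E with a critical value set before database lock by simulation under the null, using the actual accrual and number treated. For PFS, simulate with the scan schedule and the mITT count.
3. If (O+E)/2 is used uncalibrated, confirm its size by the same simulation, particularly if accrual took under 12 months.
4. Quote the section 9.1 power for the test that will be run, with the accrual period stated.

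The cost is wording in two documents and a little simulation work. No subjects or data are added. The one downside is the possible slight excess over 10% with short accrual, which the simulation in item 3 would detect.
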